10.5 SAFETY ANALYSIS

All safety analyses will be performed on the safety analysis population based on all available data by the three study groups separately.

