2 STUDY OBJECTIVE

First, to compare safety and effectiveness outcomes for canaloplasty and trabeculotomy using the OMNI Surgical System to implantation of the iStent inject in lowering intraocular pressure (IOP) in pseudophakic eyes with open angle glaucoma (OAG), and second, to compare safety and effectiveness outcomes for canaloplasty alone (using the OMNI Surgical System) to implantation of the iStent Inject in lowering intraocular pressure (IOP) in pseudophakic eyes with open angle glaucoma (OAG).

Objective 1:

The first objective is to evaluate, if for pseudophakic eyes with OAG, OMNI (canaloplasty AND trabeculotomy), is superior in lowering IOP to iStent inject.

Mean change in **unmedicated** DIOP from baseline at the 12-month postoperative examination will be used as a primary effectiveness endpoint to evaluate superiority of OMNI (canaloplasty AND trabeculotomy) compared to iStent inject in lowering IOP in pseudophakic eyes with OAG.

Objective 2:

The second objective is to evaluate if canaloplasty alone is non-inferior in lowering IOP (with a non-inferiority margin of 1.5 mmHg for comparing mean unmedicated diurnal IOP reduction at 12 months postoperative) to the iStent inject.

Mean change in **unmedicated** DIOP from baseline at the 12-month postoperative examination will be used as a primary effectiveness endpoint to evaluate non-inferiority of OMNI canaloplasty compared to iStent inject in lowering IOP in pseudophakic eyes with OAG.

The hypothesis is that the combined canaloplasty + trabeculotomy will be superior to iStent Inject and canaloplasty alone will be non-inferior to iStent Inject in lowering the IOP. Unmedicated diurnal IOP will be used to measure the change in the IOP as the primary effectiveness endpoint. The statistical approach is described in detail in Section 10 of this protocol. Diurnal IOP takes into consideration the fluctuations in IOP throughout the day and medication washout allows for isolating the effect of study treatments (1. Canaloplasty + Trabeculotomy, 2. Canaloplasty alone and 3. Trabecular bypass shunt i.e. iStent inject).

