6.2 SAFETY ENDPOINTS

- Rates of ocular adverse events (AE) (intraoperative, postoperative)
- Reduction in best corrected distance visual acuity (BCDVA) from screening
- Secondary Ocular Surgical Interventions, including laser, for IOP control

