10.4.4 OTHER EFFECTIVENESS ENDPOINTS

The statistical analyses for the other effectiveness endpoints will be based on the available data of the AT population. The percent change in unmedicated DIOP from baseline at 12 months will be calculated for each study eye as

$$\% \text{ change} = \frac{(12\text{-month unmedicated DIOP} - \text{Baseline unmedicated DIOP})}{(\text{Baseline unmedicated DIOP})} \times 100\%.$$

The number and percent of subjects achieving $\geq 20\%$ reduction in unmedicated DIOP from baseline at 12 months (i.e., 12-month responder) will be calculated. The exact 95% confidence interval of the 12-month responder rate will be calculated by the binomial distribution for each study group separately. The difference in the 12-month responder between OMNI (canaloplasty AND trabeculotomy) and iStent inject groups and the corresponding 95% confidence interval per normal distribution will be calculated. The same statistics will be provided for the difference in the 12-month responder between OMNI (canaloplasty alone) and iStent inject groups. The same statistical methods will be used to summarize the subjects with an unmedicated DIOP between 6 and 18 mmHg

inclusive at 12 months.

The descriptive statistics for the continuous variables will be used to summarize the change in number of ocular hypotensive medications used from screening to 12 months. The ANOVA with study treatment group (three groups) as the factor will be used to compare the mean difference in the change in number ocular hypotensive medications used from screening to 12 months. The mean difference between OMNI (canaloplasty AND trabeculotomy) and iStent inject groups and that between OMNI (canaloplasty alone) and iStent inject groups will be evaluated using Dunnett's test. The same methods will be used to analyze the percent change in unmedicated DIOP from baseline to 12 months.

The analyses described in this section are exploratory in nature.

[REDACTED]

[REDACTED]

[REDACTED]

10.4.5 [REDACTED]

[REDACTED]

[REDACTED]

[REDACTED]

[REDACTED]

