10.5.1 ADVERSE EVENT

AE will be classified as pretreatment, intraoperative, or postoperative. The number and the percent of eyes reporting at least 1 AE of a given type will be summarized.

Additionally, the number of reports of each type of AE will be provided.

Each AE will be summarized by incidence, percentage and the corresponding 95% confidence interval.

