10.5.2 BEST CORRECTED DISTANCE VISUAL ACUITY (BCDVA)

BCDVA data collected at the subject Baseline, and the Week 1, 1, 3, 6, and 12 month postoperative visits. The number and percent of eyes reporting with BCDVA of 20/20 or better, 20/25 or better, 20/32 or better, 20/40 or better, worse than 20/40 to 20/80 worse than 20/80 to 20/200, and worse than 20/200 at each visit will be summarized. Also, shift tables from baseline will be presented with counts, percentages, and 95% confidence intervals.

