10.5.3 OTHER SAFETY OUTCOMES

The number and percent of eyes reported with each kind of slit lamp findings, gonioscopy findings, and dilated fundus examination findings at each visit will be provided.

The descriptive statistics for the continuous variables will be derived for the visual field mean deviation (MD) and pattern standard deviation (PSD).

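### The general objective is to compare safety with iStent inject, but Section 10.5 prespecifies only per-arm safety summaries and no between-arm estimate

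*Combined protocol and SAP*

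**What the plan says.** Section 2 states the first general aim as "to compare safety and effectiveness outcomes for canaloplasty and trabeculotomy using the OMNI Surgical System to implantation of the iStent inject" and the second as "to compare safety and effectiveness outcomes for canaloplasty alone (using the OMNI Surgical System) to implantation of the iStent Inject". The title and the objectives row of the synopsis also promise a safety comparison.

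Section 6.2 lists three safety endpoints: ocular adverse event rates, reduction in BCDVA from screening, and "Secondary Ocular Surgical Interventions, including laser, for IOP control".

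Section 10.5 says that all safety analyses use the safety population and are "based on all available data by the three study groups separately". The subsections then give:
- 10.5.1: "Each AE will be summarized by incidence, percentage and the corresponding 95% confidence interval".
- 10.5.2: acuity categories at each visit, and "shift tables from baseline will be presented with counts, percentages, and 95% confidence intervals".
- 10.5.3: "The number and percent of eyes reported with each kind of slit lamp findings, gonioscopy findings, and dilated fundus examination findings", plus descriptive statistics for visual field indices.

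For exploratory effectiveness, Section 10.4.4 gives per-arm responder rates with exact intervals and then goes a step further: "The difference in the 12-month responder between OMNI (canaloplasty AND trabeculotomy) and iStent inject groups and the corresponding 95% confidence interval". It asks for the same for canaloplasty alone against iStent inject.

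**The concern.** A comparative aim needs an analysis that yields a contrast. Section 10.5 names no difference, ratio, test or margin against iStent inject. The authors did specify a contrast for responder rates that they call exploratory, so its absence for safety is a visible mismatch within the plan.

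What is at stake is prespecification. Under Section 5.2, the investigator, site staff, sponsor clinical personnel and subject all know the assignment after randomisation. If safety contrasts are wanted in the report, someone will have to choose the endpoints, the loss-of-acuity threshold and the interval method later, possibly with per-arm results in hand. A report that follows 10.5 literally would give no measure of how precisely the arms are distinguished on safety.

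**Working it through.** **1. Aim against analysis.** No arithmetic applies here; the sections are set side by side.

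| Item | Per-arm summary | Difference from iStent inject with interval |
|---|---|---|
| Responder rates (10.4.4, exploratory) | yes | yes, both OMNI arms |
| Ocular AEs (10.5.1) | yes, with 95% interval | none |
| BCDVA (10.5.2) | yes, shift tables with 95% interval | none |
| Secondary IOP interventions (6.2) | no paragraph in 10.5 | none |

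**2. Could redaction explain it?** The contents list shows 10.5.1, 10.5.2 and 10.5.3 under Safety Analysis. All three appear in the text with no redaction mark. The blacked-out Sections 10.4.1 and 10.4.5 are titled as effectiveness analyses.

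**3. The plan's sample size.** From 137 completers per arm and 10% dropout (Section 5.1): 137 / 0.9 = 152.2, rounded up to 153; 3 × 153 = 459; 3 × 137 = 411. The stated figures reproduce. The 137 itself cannot be re-derived because its inputs are redacted.

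**4. Precision of the missing contrast.** The documents give no safety event rates, so the rates below are assumptions. With equal true rate p and n per arm, the Wald 95% half-width of a risk difference is 1.96 × √(2p(1−p)/n). For p = 0.10 and n = 153: 1.96 × √(0.18/153) = 0.067, or 6.7 points.

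| Assumed rate in both arms | n = 153 per arm | n = 137 per arm |
|---|---|---|
| 2% | ±3.1 points | ±3.3 points |
| 5% | ±4.9 | ±5.2 |
| 10% | ±6.7 | ±7.1 |
| 20% | ±9.0 | ±9.5 |
| 30% | ±10.3 | ±10.9 |

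A Miettinen-Nurminen interval would differ somewhat from these Wald values, mainly at low rates.

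**5. Why per-arm intervals do not stand in for the difference.** Take assumed counts of 8/153 (5.2%) and 23/153 (15.0%). The exact per-arm 95% intervals are 2.3% to 10.0% and 9.8% to 21.7%, which overlap. The difference is 15.0 − 5.2 = 9.8 points. Its standard error is √(0.052×0.948/153 + 0.150×0.850/153) = 0.034, so the 95% interval is 9.8 ± 6.7, or 3.1 to 16.5 points. The direct contrast carries information that the two separate intervals do not show.

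**6. What the trial can resolve.** At 153 per arm and two-sided 0.05, power is about 38% for 5% against 10%, 69% for 10% against 20%, and 83% for 5% against 15% (all assumed rates). This supports estimation rather than testing.

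**The case against.** The strongest reply is that nothing formal hangs on safety. The paragraphs headed Objective 1 and Objective 2 concern IOP only, Section 10.1 frames the study goal and alpha split in IOP terms, and the synopsis judges study success on the primary effectiveness endpoint. Side-by-side rates from concurrent randomised arms are already a descriptive comparison, and a reader can compute a difference from the counts. All of this stands, and it limits the point to a reporting and prespecification gap.

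Three stronger readings are tempting, and the documents do not support them:
- A reader might infer that safety is never compared at all. Per-arm tables permit an informal comparison; what is absent is a specified estimate with its uncertainty.
- A reader might infer that safety will be judged by whether per-arm intervals overlap, so that excess harm is hidden. The plan adopts no such rule. The example in the working shows only that separate intervals are no substitute for a difference.
- A reader might infer that secondary interventions fall outside the plan. Section 8.7 keeps these subjects in the safety endpoint analyses until withdrawal, and Section 10.6 lists the endpoint among the interim safety outcomes. Only an analysis paragraph in 10.5 is missing.

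It is also fair to say that a risk difference in BCDVA loss cannot be calculated yet. The visible text gives no threshold for loss, and the safety population is grouped by actual treatment (10.2.1), so a contrast there is not strictly a randomised one. Both points shape the fix.

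**Conclusion.** The point holds as a mismatch between a stated comparative safety aim and a per-arm safety analysis. It should be corrected, but it does not threaten the primary conclusions, since no visible hypothesis, margin or success criterion depends on safety.

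If the contrast were added, its 95% half-width would be about 3 to 10 percentage points at 153 per arm, and about 3 to 11 at 137. These figures rest on assumed equal true rates of 2% to 30% and a Wald approximation. At an assumed rate of 5% the half-width is about as large as the rate itself, so the estimates would be informative for common events and imprecise for rare ones.

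**What to change.** In Section 10.5, add for each OMNI arm against iStent inject the risk difference with a 95% interval (for example Miettinen-Nurminen) for:
- any ocular adverse event;
- BCDVA loss, with a threshold prespecified by the sponsor, stating the reference visit and whether the posterior capsule opacification rule in Section 10.6 also applies to the final analysis;
- secondary IOP-lowering surgery or laser, with a paragraph naming its analysis and denominator;
- optionally, serious ocular adverse events, which are not a separate endpoint in Section 6.2.

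Label these as descriptive estimates with no multiplicity claim. Repeat them by randomised group as a check on the actual-treatment grouping. If the sponsor does not want a contrast, the coherent alternative is to reword the general objective so that it describes safety rather than compares it.

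The cost is one endpoint definition, a short paragraph and one extra table, with no new subjects or data. The downside is wide intervals for rare events, which the report should state plainly.

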10.5.1 ADVERSE EVENT

AE will be classified as pretreatment, intraoperative, or postoperative. The number and the percent of eyes reporting at least 1 AE of a given type will be summarized.

Additionally, the number of reports of each type of AE will be provided.

Each AE will be summarized by incidence, percentage and the corresponding 95% confidence interval.

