8.4.6 MONTH 12 (DAYS 330 TO 420)

The Month 12 visit is the final visit for any subjects that are not currently on any ocular hypotensive medications. For patients on medications, all assessments except the DIOP will be completed (listed below for 9 am), however, depending on the medications used, will return in from 5 to 30 days following medication washout for the DIOP assessment.

[figure not shown]

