8.4.7 MONTH 12 WASHOUT VISIT (DAYS 330 TO 420)

The Month 12 Washout visit is only intended for subjects presenting at the Month 12 visit on ocular hypotensive medication. This visit is conducted on the completion of medication washout for the purpose of obtaining an unmedicated IOP.

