9 ADVERSE EVENTS (AE)

Adverse Events are defined below. AE that occurred in the study eye during the trial, whether they are considered to be device related or not, must be documented in the subject medical records and will be collected on the CRF. Date of the event, its severity, treatment (if any), and the assessed relationship of the event to the study device will be recorded on the Adverse Event Form (AEF). Conditions which existed prior to subject enrollment do not need to be recorded as AE unless they increase in severity or frequency during the study.

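### Adverse events from the terminal washout, which only subjects medicated at Month 12 undergo, are pooled into the single postoperative class, so per-arm AE rates may not be like for like

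*Combined protocol and SAP*

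**What the plan says.** - **Who is observed after Month 12.** Section 8.4.6: "The Month 12 visit is the final visit for any subjects that are not currently on any ocular hypotensive medications". Section 8.4.7: "The Month 12 Washout visit is only intended for subjects presenting at the Month 12 visit on ocular hypotensive medication". Section 8.4.6 has medicated subjects complete everything but the diurnal IOP at Month 12 and come back 5 to 30 days later. Section 5.1 counts this terminal washout as part of participation.
- **What is collected.** Section 9: "AE that occurred in the study eye during the trial, whether they are considered to be device related or not, must be documented".
- **What is analysed.** Section 10.5: "All safety analyses will be performed on the safety analysis population based on all available data by the three study groups separately". Section 10.5.1 has three classes ("AE will be classified as pretreatment, intraoperative, or postoperative") and a crude measure: "The number and the percent of eyes reporting at least 1 AE of a given type will be summarized", with 95% confidence intervals. No visible text sets a Month 12 cut-off, a terminal-washout class or an exposure-adjusted rate.
- **A conflict on timing.** The washout text in section 8.4.1 places the second washout before the Month 12 visit, whereas 8.4.6 and 8.4.7 place it after. Both visits carry the same window, days 330 to 420.

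**The concern.** Being on medication at Month 12 is an outcome of treatment. Section 8.6 triggers rescue medication on postoperative IOP, and section 6.1 lists change in medication count as an effectiveness endpoint. If the arms differ in that share, they differ in how many eyes go through an off-drug period at the end of the study, when pressure may rise because drug was stopped. Events from that period enter the same postoperative percentage as those of the preceding 12 months.

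The plan treats washout as a period of some risk: section 7.2 excludes subjects for whom it would be hazardous, and section 8.4.1 allows a safety IOP check midway. Section 5 uses washout to remove drug confounding from effectiveness, but nothing visible does the corresponding job for safety. AEs of the pre-baseline washout fall into the pretreatment class; the terminal washout has no class of its own.

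At stake are the per-arm rates of ocular AEs and secondary IOP interventions (section 6.2). Comparing safety is part of both objectives in section 2.

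**Working it through.** **1. The plan's own figure.** Section 5.1 gives participation of about 12 months 5 days to 14 months. With a month of 365.25/12 = 30.44 days:
- 5-day washout before baseline only: (365.25 + 5)/30.44 = 12.16 months.
- 28-day washout before baseline only: (365.25 + 28)/30.44 = 12.92 months.
- 28 days before baseline and 28 days at the end: (365.25 + 56)/30.44 = 13.84 months; with 30 + 30 days, 13.97 months.

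The upper figure fits best when a terminal washout is added after Month 12, as 8.4.6 and 8.4.7 describe.

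**2. Inputs.**
- From the documents: 153 subjects per arm (section 5.1); minimum washout 5 to 28 days (Table 2); both visit windows days 330 to 420, midpoint 375.
- Assumed, because the documents do not give them: 20-30% medicated at Month 12 in one arm and 40-50% in another; probability q of 5-20% that a washed-out eye has its first event of a given type during washout.

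**3. Incidence.** Arm difference = (p2 - p1) x q.
- Smallest gap: 0.40 - 0.30 = 0.10. Then 0.10 x 0.05 = 0.005, or 0.5 points (0.005 x 153 = 0.8 eyes).
- Largest gap: 0.50 - 0.20 = 0.30. Then 0.30 x 0.20 = 0.06, or 6.0 points (0.06 x 153 = 9.2 eyes).
- Example with a 5% background rate in both arms, 20% versus 40% medicated and q = 10%: 1 - 0.95 x (1 - 0.02) = 6.9% versus 1 - 0.95 x (1 - 0.04) = 8.8%.

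**4. Time under observation.** Arm difference in mean days = (p2 - p1) x washout length.
- Smallest: 0.10 x 5 = 0.5 day, 0.5/375 = 0.13% of follow-up.
- Largest: 0.30 x 28 = 8.4 days, 8.4/375 = 2.2%.
- The shared window reduces this. If exits of unmedicated subjects are spread evenly over days 330 to 420, their mean is day 375. If a washout of d days must end by day 420, medicated subjects exit on average at (330 + 420 - d)/2 + d = 375 + d/2. The gain is then half of d: 2.5 days for a 5-day washout, 14 days for a 28-day one.

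Time is the minor part. The weight lies in the type of event.

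**5. Against ordinary precision.** The 95% half-width for one arm of 153 is 1.96 x sqrt(0.05 x 0.95/153) = 3.5 points at a 5% rate and 4.8 points at 10%. Only the upper part of the 0.5 to 6 point range exceeds this.

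**The case against.** A reader might infer that the arm with more medicated subjects must, by construction, end up with more AE time and more events. The documents do not support that.

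- **Time.** Because the two visits share a window, an unmedicated subject seen on day 400 is followed longer than a medicated one seen on day 340 and washed out by day 368. On the wording of section 8.4.1 the extra time could vanish, although an off-drug period confined to medicated subjects would remain.
- **Withdrawals.** Section 8.7 withdraws subjects after a secondary IOP procedure. A less effective arm may have more of these too, which shortens its follow-up.
- **Events.** Section 9 does not require pre-existing conditions to be recorded unless they worsen in severity or frequency, and every eye entered with an unmedicated diurnal IOP of at least 22 mmHg. A return towards that level may not count as an AE. No visible passage supports any particular washout event rate, and some of the AE text and the washout-visit procedures are not available to read. AE capture at that visit is therefore inferred from sections 5.1, 9 and 10.5.
- **Consequence.** No between-arm AE test is visible, and the primary endpoint does not depend on AE classes. Event dates are recorded, so washout events could be identified later in any case.
- **Remedy.** Dropping post-Month 12 events from the main counts would depart from the commitment to use all available data.

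All of this limits the size and certainty of the point. What remains is that off-drug ascertainment is tied to a post-randomisation outcome and that the plan does not separate it. The absence of a test does not settle the matter, since readers will compare the per-arm percentages and intervals. In an open-label trial (section 5.2), the split is better specified before the data are seen.

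**Conclusion.** The point holds in a limited form. As sections 8.4.6 and 8.4.7 are written, a study-mandated off-drug period with a further visit exists only for subjects medicated at Month 12. Sections 10.5 and 10.5.1 would then count its study-eye AEs with all other postoperative events. Per-arm AE rates may therefore differ for reasons other than the device.

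Under the assumed inputs the arm difference runs from 0.5 to 6 percentage points, and the difference in mean follow-up from 0.5 to 8.4 days, less on average because of the shared window. Both ranges rest on medicated shares and a washout event probability that the documents do not supply. The net direction is not established. The effect is on descriptive safety results only. This is a worthwhile, inexpensive improvement to the analysis plan, not a flaw in the trial's main conclusion.

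**What to change.** 1. In section 10.5.1, split postoperative AEs and secondary IOP interventions by onset date into:
   - (a) surgery to the start of the terminal washout, or to the Month 12 visit for subjects without one. This is the like-for-like comparison between arms.
   - (b) the terminal washout, per arm, with the number of eyes washed out as denominator and every event listed.
2. Keep the all-available-data total beside the split, so that no event leaves the safety record.
3. Reconcile the washout text in section 8.4.1 with sections 8.4.6 and 8.4.7, so that the start of the terminal washout, and hence the cut-off, is defined.

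Cost: a few lines of analysis text and one extra table with a small denominator. AE dates are already recorded. On the 8.4.6 reading the cut-off is the Month 12 visit date; on the 8.4.1 reading, confirm that the date of stopping medication is captured.
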